10.1. Access to Records

The records are available for direct inspection, verification, and copying, as required by applicable laws and regulations, by officials of the regulatory health authorities (FDA and others). The investigator shall comply with applicable privacy and security laws for use and disclosure of information related to the research set forth in this protocol.

10.2. Patient Privacy

To maintain patient confidentiality, all study reports, and communications relating to the study will identify patients by assigned subject numbers. The FDA (or other regulatory authority) or the Institutional Review Board may also request access to all study records, including source documentation, for inspection.

As applicable, in accordance with HIPAA and associated privacy regulations, a patient's authorization to use personally identifiable health information may be required from each patient before research activities begin. This authorization document shall clearly specify which parties will have access to a patient's personal health information, for what purpose, and for how long.

10.3. Record Retention

The PI will maintain all study records according to GCP guidelines.

11. Withdrawal from Study

Patients should immediately be withdrawn from the study for any of the following reasons.

- A condition or adverse event that would prevent the patient from performing the

- specified measurements in the protocol
- At the discretion of the patient
- At the discretion of the Investigator, if deemed appropriate, for any reason

If a patient is withdrawn because of an adverse event, the patient will be followed and treated by the Investigator until the abnormal parameter or symptom has resolved or stabilized. The adverse events must be followed to resolution and the follow-up evaluations should be performed when the patient has stabilized.

Any patient that is withdrawn from the study within the first two weeks due to technical or training reasons will be replaced.

If for any reason a patient does not complete the study, the reason will be entered on the CRF. All patients are free to withdraw from participation at any time, for any reason, specified or unspecified, and without prejudice. The Investigator must record the reason for the early termination.

12. Concomitant Medications

Patients can remain on all prescribed medications. Medications can be changed during the study when clinically indicated by the study PI or patient provider.

13. Statistical Considerations:

This is a technical evaluation intended to determine if remote patient monitoring can be integrated into the home monitoring of patients with COPD and determine both the acceptance and value of its use. The sample size is not powered or intended to establish statistically significant differences from historic experience. The adherence and utilization of the platform, as defined by the physiologic and QoL measurements, will be helpful in establishing guidance for future efficacy trials.

Nevertheless, descriptive characteristics of the patients prior to, during, and at the end of the study will be tabulated. Using the full analytical set (FAS), specific variables (demographics and clinical variables, baseline maintenance and rescue inhaler use, and modified Medical Research Council Score) will be summarized using descriptive measures (mean and standard deviation, min, max, median) and graphical displays (boxplots, histograms) as appropriate.

Differences between important continuous variables at two specific times will be evaluated with the two-sided paired t-test ($P<0.05$). Important categorical events such as changes in FEV1, Inspiratory Capacity, QoL, medication adherence, rehospitalization and incidence of adverse events will be evaluated by constructing 95% confidence limits in their incidence, and also with descriptive statistics. In addition, the results will be used to identify technological deficiencies and provide data to inform the power requirements for future studies.

Primary Endpoint Definitions

The first primary endpoint variable for this study is the change from baseline in Total Score of COPD Assessment Test (CAT). The total CAT score is calculated by summing the scores of all items and ranges from 0 to 40, higher scores indicating severe condition. The change will be calculated as the CAT score at Week 12 minus the CAT score at Enrollment. A negative change in CAT score will indicate an improvement in patient status.

The second primary endpoint variable for this study is adherence to performing scheduled measurements and responding to scheduled questionnaires. For each subject the adherence will be recorded based on the data uploaded to the CarePortal. The adherence percentage will be calculated by the difference in recorded measurements and answered questionnaires versus the scheduled measurements and questionnaires.

Analysis of Primary Endpoints

The primary outcomes will be reported as proportions with 95% confidence intervals, on the FAS.

Secondary Endpoint Definitions

The prespecified secondary endpoints for this study will include:

- Participant satisfaction survey scores at 3 months (Time frame: 3 months) defined as the percentage of participants with score of 4 or higher on individual survey domains. A satisfaction survey (investigator-developed, 15 questions, each question is graded on a scale of 1-5, 1 being not at all and 5 being extremely) will be used to measure home spirometry and table ease and usefulness.
- Rate of self-reported COPD exacerbations (Time frame: 3 months) defined as the 30-day COPD exacerbation rate, defined as the mean number of events/30 days of follow-up (using three months of follow-up data). COPD exacerbation events are defined as self-reported COPD exacerbations requiring treatment with antibiotics or steroids.

Analysis of Secondary Endpoints

The secondary endpoints will be reported as proportion with 95% confidence interval of participants with score of 4 or higher on individual survey domains of patient satisfaction summary score; Descriptive analysis of patient satisfaction summary scores will include mean (SD), median (IQR), range of scores.

For the COPD exacerbation analyses, the proportion of patients with COPD exacerbations and the rate of exacerbations occurring during follow-up will be reported along with 95% CI. A patient will be considered censored for exacerbations at the time of the last documented visit, the end of the study, or death (whichever occurs earlier), if they did not experience an exacerbation before.

Exploratory Endpoints Definitions

The study contains exploratory endpoints to examine individual components of the monitoring functions and their impact. These include:

- Rate of self-reported COPD exacerbations stratified by FEV1 and defined as the 30-day COPD exacerbation rate, defined as the mean number of self-reported COPD exacerbations

requiring treatment with antibiotics or steroids per 30 days of follow-up (averaged using 3 months of follow-up data), stratified by FEV1 (separately <50% predicted and >=50% predicted).

- Home spirometry measurement collection adherence defined as the percentage of participants achieving >50% completion of spirometry measurements over three months.
- Home pulse oximetry measurement collection adherence defined as the percentage of participants achieving >50% completion of pulse oximetry over three months.
- Home questionnaire collection adherence defined as the percentage of participants achieving >50% completion of home questionnaires over three months.
- Quality of home forced spirometry measures defined as the percentage of forced home spirometry measurements that meet ATS quality standards
- Change from baseline on COPD Assessment Test (CAT) Total Score defined as the CAT scores measured at baseline, week 4, week 8 and week 12 and the median (SD) change in CAT score from baseline will be calculated at each time point.
- Inspiratory Capacity variability defined as the coefficient of variation will be calculated by dividing standard deviation of Inspiratory Capacity values by the mean of the inspiratory capacity values. Inspiratory capacity measured via slow vital capacity maneuver will be performed at home five days per week during duration of study.
- Inspiratory Capacity before, during and after COPD exacerbations defined as the overall median Inspiratory Capacity reported at three time intervals: the week before COPD exacerbation, the week of COPD exacerbation, and the week after COPD exacerbation.
- Number of clinical interventions defined as the total number of clinical interventions per participant over study duration. Clinical interventions will be categorized into one of three types (phone contact, clinic visit, referral to Emergency Department).
- Type of clinical interventions defined as the percentage of type of clinical intervention across all study participants. Clinical interventions will be categorized into one of three types (phone contact, clinic visit, referral to Emergency Department).
- Suboptimal peak inspiratory flow measurements defined as the percentage of peak inspiratory flow measurements <3.27 liter/sec obtained on forced spirometry maneuvers.
- Maintenance inhaler adherence defined as the adherence will be defined by average number of days per week (range 0-7) participant reports maintenance inhaler use.
- Change from baseline in maintenance inhaler adherence defined as the change from baseline to 3 months in maintenance inhaler adherence. Adherence will be defined by number of days per week (range 0-7) participant reports maintenance inhaler use.
- Change from baseline in rescue inhaler use defined as the change from baseline to 3 months in rescue inhaler use. Rescue inhaler use will be categorized at baseline and 3 month visit as not at all, once a week or less, 2-3 times per week, 1-2 times per day, 3 or more times per day.

Analysis of Exploratory Endpoints

The exploratory endpoints will be analyzed as described below. The hypothesis testing of these additional secondary efficacy endpoints is considered exploratory. All tests with p value < 0.05 will be interpreted nominally as statistically significant.

- For stratified COPD exacerbation analyses, the proportion of patients with COPD exacerbations and the rate of exacerbations occurring during follow-up will be reported along with 95% CI stratified by FEV1 severity (<50% predicted: >=50% predicted).
- Individual home assessment component adherence will be reported as proportions with 95% confidence intervals
- Quality of home forced spirometry measures will be reported as proportions with 95% confidence intervals
- Descriptive analysis of change from baseline to weeks 4, 8 and 12 on CAT Total score including mean (SD), median (IQR), range
- Descriptive analysis of Inspiratory Capacity measurements, including mean (SD), median (IQR), range, coefficient of variation
- The overall median of Inspiratory Capacity in the week before, of, and after each exacerbation will be calculated and compared using Kruskall-Wallis testing.
- The total number and distribution of type of intervention (phone contact, clinic visit, referral to Emergency Department) will be summarized in tabular format
- The proportion of suboptimal peak inspiratory flow measurements (defined as <3.27L/sec) will be reported with 95% CI. Additional exploratory analyses include distribution of peak inspiratory flow measurements along with proportions of alternative thresholds.
- Descriptive analysis of overall maintenance inhaler adherence including mean (SD), median (IQR), range, proportion and 95% CI of participants with >50% adherence
- Descriptive analysis of change from baseline to week 12 on number of days per week of maintenance inhaler adherence including mean (SD), median (IQR), range
- Tabular summary of overall rescue inhaler use (categorized into not at all, once a week or less, 2-3 times per week, 1-2 times per day, 3 or more times per day)
- Comparative analysis (chi square) of distribution of categorical responses to rescue inhaler use comparing baseline to 12 week visit
- Tabular summary of number and type of SAE

14. Safety Monitoring

As this study is deemed low risk, using technology frequently prescribed for use by COPD patients at home, oversight for this feasibility study will be conducted by the PI ([name]). The PI will monitor data to ensure the safety of participants. Only treatment-related serious adverse events (SAEs) will be reported to the IRB using the Adverse Event Template Form, per institutional and national guidelines within one business day of notification of the event. Hospitalization for COPD exacerbation will be considered an SAE. SAEs will be tracked for 30 days following termination of the study.

15. Administrative Requirements

15.1. *Ethical Considerations*

The study will be conducted in accordance with the ethical principles founded in the Declaration of Helsinki, and according to local applicable laws and regulations. The institutional

review board (IRB) will review all appropriate study documentation to safeguard the rights, safety, and well-being of the patients.

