4.2. Study Design

This is a prospective, open label trial evaluating home telemonitoring for patients with COPD and a history of increased exacerbation risk. The purpose of this study is to determine whether automated home monitoring of medication compliance and biometric parameters (FEV1, FVC, PIFR, IC, pulse oximetry, and symptoms) is acceptable to patients, can improve adherence, and may improve clinical outcomes and reduce exacerbations and avoidable 30-day readmissions. Slow spirometry will be performed Sundays, Mondays, Wednesdays, Fridays and Saturdays. Forced spirometry will be performed Tuesdays and Thursdays.

5. Study Endpoints

5.1. The specific Primary Endpoints of this study are:

- Adherence to measurement collection
- Quality of Life scores

5.2. The specific Secondary Endpoints of this study are:

- Variability in slow spirometry and correlation of change in slow spirometry values with COPD exacerbation
- Patient satisfaction with the monitoring system
- Thirty (30) day exacerbations
- Total number of clinical interventions by type (what the medical staff does in response to the telemonitoring)
- Ability for early identification of loss of DPI effectiveness
- Adherence to taking prescribed medications

6. Selection of Study Population

Eligible participants include those being managed for COPD by the UNC Hospitals Pulmonary Specialty Clinic in Chapel Hill, NC and who have been identified to be at a higher risk of exacerbation of their COPD. We plan to enroll twelve (12) patients for three (3) months of monitoring each. The study will be at a single center and anticipated to be completed within nine (9) months.

6.1. Inclusion Criteria:

- Male or Female patients
- 40 to 80 years of age
- English
- Spirometry confirmed COPD (post-BD FEV1/FVC<0.70) and post-BD FEV1% predicted <80% at screening visit. (Target 50% of recruitment with post-BD FEV1<50% predicted (severe obstruction). Spirometry must have been collected within 24 months prior to screening.
- Increased COPD exacerbation risk defined as either of the following in the prior 12 months:
 - One hospitalization for COPD exacerbation
 - Two outpatient COPD exacerbations requiring treatment with steroids and/or antibiotics
- Signed informed consent

6.2. Exclusion Criteria:

- Unable to perform spirometry on their own following training.

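### Section 11 withdraws patients from the whole study when illness stops the measurements and requires no outcome data afterwards, so data can go missing for reasons tied to the outcome

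*Combined protocol and SAP*

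**What the plan says.** Section 11 opens with "Patients should immediately be withdrawn from the study for any of the following reasons". The first reason listed is "A condition or adverse event that would prevent the patient from performing the" measurements laid down in the protocol. The text sets no duration, severity or permanence, and the withdrawal is from the study, not only from device use.

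For withdrawals due to an adverse event, Section 11 adds: "The adverse events must be followed to resolution and the follow-up evaluations should be performed when the patient has stabilized". It does not say what those evaluations are. Replacement is narrow: "Any patient that is withdrawn from the study within the first two weeks due to technical or training reasons will be replaced". A patient lost to illness is therefore not replaced.

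Several outcomes need data from after such an event:

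- **CAT (primary):** Section 13 takes Week 12 minus Enrollment. The synopsis counts a fall of at least 2 points as a response.
- **Exacerbations (secondary):** Section 13 uses a rate per 30 days from three months of follow-up, and the proportion of patients with an event.
- **Inspiratory capacity (exploratory):** Section 13 compares "the week before COPD exacerbation, the week of COPD exacerbation, and the week after COPD exacerbation".
- **Satisfaction (secondary):** Sections 9.2.10 and 17 collect the usability questionnaire only at the final call, in Week 13.

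Section 13 reports the primary outcomes on the full analysis set (FAS), but the set is never defined and there is no rule for missing data. Section 14 classes hospitalization for a COPD exacerbation as an SAE.

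**The concern.** Entry requires a hospitalization or two treated outpatient exacerbations in the previous year (Section 6.1), so exacerbations during three months of monitoring are expected. One severe enough to stop spirometry satisfies the withdrawal rule as written. The patient then leaves the study because of the disease event that the study is meant to describe, and no outcome has to be collected afterwards.

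At stake is whether the Week 12 CAT, the post-event inspiratory capacity and the satisfaction scores describe all twelve patients or mainly those who stayed well enough to measure. Section 13 intends the results to inform the power of later studies, so a systematic error would carry forward.

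**Working it through.** **Plan's own figure.** The sample size is 12: "We plan to enroll twelve (12) patients for three (3) months of monitoring each". No effect size, SD, power or dropout rate is given, and Section 13 says "The sample size is not powered or intended to establish statistically significant differences from historic experience". There is no calculation to reproduce, so the check sizes the consequence of the rule.

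**1. How many patients could be withdrawn this way.** Assumptions, not document figures: exacerbation rate r = 1 to 3 per patient-year; share s = 10 to 40% that prevent measurement. Monitoring lasts 12 weeks = 84 days.

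P(withdrawn by Week 12) = 1 − exp(−r × s × 84/365.25)

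| r | s | P | Expected of 12 | P(at least one) |
|---|---|---|---|---|
| 1 | 10% | 2.3% | 0.27 | 24% |
| 2 | 20% | 8.8% | 1.05 | 67% |
| 2 | 40% | 16.8% | 2.02 | 89% |
| 3 | 40% | 24.1% | 2.89 | 96% |

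**2. CAT response.** Illustration: 5 responders, none of them withdrawn (Clopper-Pearson 95% CI).

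| Withdrawn | Kept as non-responders | Dropped |
|---|---|---|
| 0 | 5/12 = 41.7% (15.2 to 72.3) | same |
| 1 | 41.7% | 5/11 = 45.5% (16.7 to 76.6) |
| 2 | 41.7% | 5/10 = 50.0% (18.7 to 81.3) |
| 3 | 41.7% | 5/9 = 55.6% (21.2 to 86.3) |

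Each dropped patient adds about 4 to 6 points. The undefined FAS leaves the choice of column open.

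**3. Exacerbations.** A daily simulation (40,000 patients per scenario) withdrew each patient at the first event that prevents measurement. With r = 2 and s = 40%, events per 30 days were:

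| | Full follow-up | Pooled events / person-time | Mean of individual rates | Fixed 84-day denominator |
|---|---|---|---|---|
| No clustering | 0.165 | 0.165 | 0.428 | 0.151 |
| Hazard tripled for 56 days after an event | 0.222 | 0.197 | 0.459 | 0.178 |

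The rate can stay the same, fall or rise, depending on the estimator and on clustering. The proportion with at least one event was identical with and without withdrawal in every scenario (36.9% in the clustered row), because the withdrawing event is itself counted.

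**4. Inspiratory capacity.** A patient withdrawn at the event supplies the week before. A patient too ill to blow supplies little in the week of the event, whether or not withdrawn. What the rule itself removes is mainly the week after, so that median would come from milder events.

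**5. Adherence (primary).** Scheduled entries: 84 spirometry + 84 oximetry + 4 CAT = 172. A patient withdrawn at day 42 with perfect compliance has 42 + 42 + 2 = 86, and 86/172 = 50.0%, which does not exceed the 50% threshold. On a denominator cut at withdrawal, the same patient scores 86/86 = 100%. The synopsis refers to all planned measurements over three months, which points to the full denominator. Section 13 compares recorded with scheduled entries and does not say whether scheduling ends at withdrawal.

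**The case against.** The strongest reply is that Section 11 does not mention exacerbations and that the rest of the plan expects patients to stay through them. Section 9.2.8 records hospitalizations during monitoring, Section 13 counts emergency referrals and wants inspiratory capacity in the week after an event, and Section 14 handles admissions as SAEs. On that reading, Section 11 means lasting inability. This is plausible, and it shows that removal at every severe exacerbation is not a settled rule. But the text says immediately and has no such limit, so staff who follow it literally would withdraw the patient. The passages need reconciling.

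Section 11 also requires adverse events to be followed to resolution, and Section 14 tracks SAEs for 30 days after the study ends. These provisions stand, so follow-up is not lost altogether. They serve safety, and neither requires a Week 12 CAT, a continuing exacerbation count or inspiratory capacity.

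Two stronger readings are tempting. A reader might infer that every resulting loss flatters the system. The documents do not support that: the withdrawing event still counts, the rate has no fixed direction of error, and on the synopsis definition early withdrawal lowers adherence. A reader might also take 2 to 4 exacerbations a year, suppose that half lead to withdrawal, and conclude that 18 to 30% of Week 12 CAT scores are lost. Nothing in the documents supports a half share. Study exacerbations are any self-reported events treated with antibiotics or steroids, which includes outpatient courses.

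Finally, this is an unpowered study of 12 patients, and the intervals above are about 57 to 65 points wide. Sampling error is larger than the shift, but it does not remove a systematic one.

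**Conclusion.** The point holds in limited form. As written, Section 11 can take patients out of the whole study at a severe exacerbation, and nothing requires outcome data afterwards, so the missing data would be related to the outcome. The likely scale is 0.3 to 2.9 of 12 patients by Week 12, resting entirely on the assumed rate and share.

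- **CAT response:** biased upward by about 4 to 6 points per patient if withdrawn patients who would not have responded are dropped; no such upward shift if they count as non-responders.
- **Inspiratory capacity:** the week-after result is the most directly exposed, though it is one exploratory endpoint.
- **Satisfaction:** scores from withdrawn patients can be lost.
- **Exacerbations:** the proportion of patients is unbiased if the withdrawing event is recorded; the rate may move either way.
- **Adherence:** the synopsis already favors the full denominator; Section 13 should say so.

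This does not undermine a descriptive feasibility study, but it should be corrected because the remedy is cheap.

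**What to change.** 1. In Section 11, separate stopping device measurements from withdrawing from the study.
2. Unless consent is withdrawn, continue the scheduled nurse calls, the Week 12 CAT (by phone if needed), exacerbation and SAE collection, and the usability survey to Week 13.
3. In Section 13, define the FAS so that these patients remain in it, and count a missing Week 12 CAT as non-response.
4. State that the adherence denominator is all measurements planned over the full 12 weeks, as the synopsis implies.
5. Name the estimator for the 30-day exacerbation rate.
6. Reconcile Section 11 with the week-after-exacerbation endpoint in Section 13. When a patient should stop or resume measurements remains a clinical decision for the study team.

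The cost is a short amendment. The calls are already in the Section 17 schedule. Adherence and CAT response may look slightly lower, and counting missing CAT scores as non-response is conservative for any withdrawn patient who did improve, which is why obtaining the score by phone comes first.

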Sample Size Justification	This is a technical evaluation intended to determine if telehealth monitoring can be integrated into the home monitoring of patients with COPD and determine both the acceptance and value of its use. The sample size is not powered or intended to establish statistically significant differences from historic experience.
Statistical Analysis	
The sample size of this technical evaluation is not powered or nor intended to establish statistically significant differences. The adherence and utilization of the platform, as defined by the physiologic and QoL measurements, will be helpful in establishing guidance for future efficacy trials. Nevertheless, descriptive characteristics of the patients prior to, during, and at the end of the study will be tabulated.
 
The study is based on two primary endpoints, adherence to home device measurement collection and baseline to Week 12 change in Total Score of COPD Assessment Test (CAT). Home device measurement adherence is described as percentage of participants achieving >50% completion of all planned device measurements (spirometry, pulse oximetry and questionnaires) over three months. Change in CAT score is defined as percentage of participants achieving ≥ 2 point decrease in CAT from baseline to three months. Additional secondary and exploratory outcomes are also identified in the full protocol.
 
The primary outcome will be reported as proportion with 95% confidence intervals. Other outcomes will be described with proportion and 95% confidence interval, rate, or descriptive summary measures as defined in the full protocol. All tests with p value < 0.05 will be interpreted nominally as statistically significant. In addition, the results will be used to identify technological deficiencies and provide data to inform the power requirements for future studies.

2. Table of Contents

1	Protocol Synopsis	2
2.	Table of Contents	5
3.	List of Abbreviations	7
4.	Introduction	8
4.1.	Background	8
4.2.	Study Design.....	8
5.	Study Endpoints	9
5.1.	The specific Primary Endpoints of this study are:.....	9
5.2.	The specific Secondary Endpoints of this study are:.....	9
6.	Selection of Study Population.....	9
6.1.	Inclusion Criteria:.....	9
6.2.	Exclusion Criteria:.....	9
7.	Study Procedures:	10
7.1.	Patient Identification and Informed Consent	10
7.2.	Study Home Equipment	10
7.3.	Study Data Platform.....	11
7.4.	Study Procedure.....	11
8.	Quality Control Measures	12
9.	Assessments.....	12

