7.3. Study Data Platform

Data collected from patients' homes will be stored on the MTI CarePortal (See Section 10), a cloud server hosted in Dublin, Ohio. This portal will monitor all data received or expected to be received and will send alerts via text and/or e-mail to the investigative team based on pre-defined thresholds. These alerts will be sent for missed spirometry sessions as well as for spirometry which falls below alert thresholds. It will also send alerts based on oxygen saturation alarm thresholds as well as missed medications or measurements or changes in their CAT score.

The platform will also:

- Remind patients to take their medications
- Remind patients to perform measurements
- Send patients helpful information
- Execute a UNC clinic established COPD Action Plan

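### Does the primary adherence percentage need a written rule for participants who leave early?

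*Combined protocol and SAP*

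**What the plan says.** The responder rule is in the synopsis, under Statistical Analysis: "percentage of participants achieving >50% completion of all planned device measurements (spirometry, pulse oximetry and questionnaires) over three months". Section 13, Primary Endpoint Definitions, gives the figure for each participant: "The adherence percentage will be calculated by the difference in recorded measurements and answered questionnaires versus the scheduled measurements and questionnaires". The source is the data uploaded to the CarePortal. Analysis of Primary Endpoints adds: "The primary outcomes will be reported as proportions with 95% confidence intervals, on the FAS". The FAS also appears earlier in Section 13 ("Using the full analytical set (FAS), specific variables"), but no sentence says who belongs to it.

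Section 11 foresees early leaving. Its first reason for withdrawal begins "A condition or adverse event that would prevent the patient from performing the" and goes on to the protocol's measurements; patient choice and investigator discretion follow. It also states: "If for any reason a patient does not complete the study, the reason will be entered on the CRF". On replacement it says: "Any patient that is withdrawn from the study within the first two weeks due to technical or training reasons will be replaced". Section 7.4 says that a participant who cannot transmit satisfactory data after one week is removed, and that another is recruited toward the planned total.

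Section 7.3 describes the portal: "This portal will monitor all data received or expected to be received". Section 13 has a censoring rule for exacerbations and no matching sentence for adherence.

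**The concern.** The primary objective is to learn whether patients will use the system, and stopping is a direct way of not using it. The Section 13 sentence, read alone, allows two denominators: everything planned for 12 weeks, or everything due up to the date of leaving. Someone who leaves early fails on the first and can pass on the second. If the text left both open, the choice could be made after the data are seen. With 12 participants, one or two such cases would visibly change the reported proportion, which is meant to inform later trials.

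The number of participants in the denominator looks open as well. People removed because they could not get the technology working bear on feasibility, and leaving them out without comment would raise the adherence figure.

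**Working it through.** The documents give no expected adherence or dropout rate, so there is no planned figure to reproduce.

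**1. Items scheduled.** Spirometry is 5 slow + 2 forced = 7 sessions a week (Section 9.2.3), which agrees with the seven a week in Section 8. Oximetry is daily (Section 17, footnote h). The CAT is due at enrollment and at weeks 4, 8 and 12 (Section 9.2.5). Active monitoring lasts 12 weeks (Section 7.4). The total is 7×12 + 7×12 + 4 = 84 + 84 + 4 = 172. More than 50% means at least 87.

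**2. Items due by the end of week w.** D(w) = 14w + 1 + floor(w/4), where the 1 is the enrollment CAT.

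| Leaves at end of week | Items due | Best possible on full count | Needed on count to leaving |
|---|---|---|---|
| 4 | 58 | 58/172 = 33.7% | 30 of 58 |
| 5 | 72 | 72/172 = 41.9% | 37 of 72 |
| 6 | 86 | 86/172 = 50.0% | 44 of 86 |
| 8 | 115 | 115/172 = 66.9% | 58 of 115 |

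A week-8 leaver passes the full count with 87 of 115 (75.7%), so the two counts disagree for 58 to 86 items done.

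**3. Does the boundary depend on what counts as an item?** Week 6 is an exact tie at 50.0%. Without the enrollment CAT it is 85/171 = 49.7%. If the three measurements on the training call (Section 7.4) count as extra items, it is 89/175 = 50.9%, a pass. Week 5 fails on each of these counts: 72/172 = 41.9%, 71/171 = 41.5%, 75/175 = 42.9%. The firm statement is therefore that leaving by the end of week 5 fails the full count; week 6 depends on the item list.

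**4. Size of the effect.** With no leavers there is none. Each reclassified leaver moves the result by 1/12 = 8.3 points. As an illustration, assume that 8 of 10 completers are adherent and that two others leave by week 5 with more than half of their due items done. Exact (Clopper-Pearson) 95% intervals are used; the plan names no method.

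- Full count: 8/12 = 66.7% (34.9 to 90.1).
- Count to leaving: 10/12 = 83.3% (51.6 to 97.9).
- Leavers left out: 8/10 = 80.0% (44.4 to 97.5).

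If instead two people are removed and replaced (assumed), 8/12 = 66.7% without them becomes 8/14 = 57.1% (28.9 to 82.3) with them kept as non-adherent.

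**5. Which count does the text support?** The synopsis speaks of everything planned and fixes the window at three months; both features describe a full-schedule denominator. The component adherence definitions in Section 13 repeat the three-month window. The Section 13 sentence gives the percentage for each participant and contradicts neither. The Section 7.3 sentence introduces text and e-mail alerts and does not define an analysis. That nothing is expected after a participant leaves is an inference that the documents do not state.

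**6. Do the replacement texts conflict?** Section 7.4 says when a participant is removed (after one week without satisfactory data). Section 11 says which withdrawals are replaced (technical or training reasons within two weeks). A removal after one week falls inside two weeks, so both can be true. Recruiting a substitute toward the total also suggests that the removed person is not one of the 12.

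**The case for a change.** The strongest case for a change is that a descriptive study's product is its estimate, so being unpowered is no excuse for leaving the primary denominator implicit. The plan says how early leaving is handled for exacerbations but not for adherence. A few sentences in Section 13 would settle the matter without new data, since uploads and reasons for non-completion are already recorded.

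Part of this stands. No sentence deals with items due after leaving, the FAS has no definition, and nothing says whether the enrollment CAT or the training-call items count. The arithmetic in steps 1 to 4 is right.

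The rest is weaker. The exacerbation endpoint is a rate per 30 days of follow-up and needs an end date for follow-up; a proportion over a fixed three-month window does not need one in the same way. The remedy would write down the count that the synopsis already describes, so the primary result would not change. A second result counted to the date of leaving, or one that adds removed participants as failures, would be extra reporting; it would not correct a rule shown to give a wrong answer. The word *difference* in the Section 13 sentence is loose, but the synopsis makes the meaning and the cut clear.

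**Conclusion.** The gap is real but it is one of missing detail, and no change to the plan is called for. An analyst who follows the synopsis uses all items planned for 12 weeks as the denominator and counts items after leaving as not done. That suits the objective, because a participant who stops by the end of week 5 is then non-adherent however complete the record was until then.

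Departing from that reading would cost 8.3 points per reclassified leaver among 12. The illustrated range of 66.7% to 83.3% rests on two assumed leavers, and its intervals overlap widely. Two details are left to the analyst: whether training-call items count, which matters only for a near-perfect participant who leaves at about week 6, and whether removed and replaced participants belong to the FAS. The replacement wording suggests that they do not.

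The conclusion assumes that the synopsis definition governs the primary endpoint, which nothing in Section 13 contradicts. It also takes into account that the study has one arm, no success threshold and no claim to statistical power.
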